8.2.3 Relationship to Study Drug

The relationship of an AE to the study drug should be determined by the investigator according to the following criteria:

- Not related: The event is most likely produced by other factors such as the subject's clinical condition, intercurrent illness, or concomitant drugs, and does not follow a known response pattern to the study drug, or the temporal relationship of the event to study drug administration makes a causal relationship unlikely
- Unlikely related: The event is most likely produced by other factors such as the subject's clinical condition, therapeutic interventions, or concomitant drugs administered to the subject and it does not follow a known response pattern to the study drug
- Possibly related: The event follows a reasonable temporal sequence from the time of drug administration, and/or follows a known response pattern to the study drug, but could have been produced by other factors such as the subject's clinical condition, intercurrent illness, or concomitant drugs
- Related: The event follows a reasonable temporal sequence from the time of drug administration, and/or follows a known response pattern to the study drug, and cannot be reasonably explained by other factors such as the subject's clinical condition, intercurrent illness, or concomitant drugs

8.3 Discontinuation due to Adverse Events

Any subject who experiences an AE may be withdrawn at any time from the study at the discretion of the investigator. Subjects withdrawn from the study due to an AE, whether serious or nonserious, may be followed by the investigator until the clinical outcome of the AE is determined. The AE(s) should be noted on the appropriate eCRFs and the subject's progress should be followed until the AE is resolved or stabilized as determined by the investigator. The sponsor and medical monitor must be notified. If the AE relates to overdose of study treatment, the Investigator's Brochure should be consulted for details of any specific actions to be taken.

8.4 Reporting Serious Adverse Events

In the event of any SAE reported or observed during the study, whether or not attributable to the study drug, site personnel will report it immediately by telephone to the sponsor, medical monitor, and SAE hotline at ICON (ICON plc Pharmacovigilance) in accordance with procedures described in the SRM and/or SAE SSP. Site personnel will follow up with a written report to the sponsor on the next working day.

SAE Report Forms will be provided to the CRU to assist in collecting, organizing, and reporting SAEs and follow-up information.

All SAEs should be followed to their resolution, with documentation provided to the sponsor, medical monitor, and ICON on a follow-up SAE Report Form.

CONFIDENTIAL

9 STATISTICAL CONSIDERATIONS

The statistical analysis will be conducted following the principles as specified in ICH Topic E9 (CPMP/ICH/363/96).

All statistical analyses will be described in a separate statistical analysis plan.

9.1 Sample Size Calculation

A total of 30 healthy, postmenopausal female subjects (n = 10 per arm) are planned for inclusion in this study. The sample size for this study is based on the desire to accurately assess the PK of estrogens and progesterone from the DARE-HRT1 IVR, is empirically derived, and supported by the PK data obtained from ovariectomized sheep. Descriptive analyses compared to oral estrogen/progesterone therapy will also be performed.

The sample sizes provided are deemed sufficient to allow for adequate assessment of the PK of the IVR (test) formulations. Dropouts may be replaced. Subjects who terminate early from the trial may be replaced to ensure an adequate number of subjects contributing to the PK for each treatment arm.

9.2 Analysis Populations

Pharmacokinetic Population: all subjects who received a full course of study treatment for their dispensed treatment and who have sufficient concentration data for determination of PK parameters (primary endpoints); data will be analyzed according to the actual study treatment received.

Safety Population: all enrolled subjects who received active treatment, i.e., inserted an IVR (and thus who were exposed to one of the IVRs) or who took at least one dose of the oral reference.

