| Time | | | | 0.5, 1, 2, 4, 8, 12, 24, and 48 hours post insertion | | | | | |
| FSH | X | | | | | | | | |
| Serology tests ^e | X | | | | | | | | |
| Drug and alcohol urine screen | X | X | | | | | | | |
| Transvaginal Ultrasound | X | | | | | | | X | |
| Urine dipstick | X | X | | | | | | X (EOS) | |
| Dispense test article(s) | | | X | | | | | | |
| Training on use of IVR | X | | X | | | | | | |
| Usability and Tolerability questionnaire | | | | | | | | X | |
| Insert Vaginal Ring (after predose PK sample) | | | X | | | | | | |
| Confirm vaginal ring placement | | | | X ^f | X | | X | | |
| PK blood samples | X | X | X (-1, -0.5, and 0 hours predose) | X (once) | X (once) | X (once) | X (0, 0.5, 1, 2, 4, 8, and 12 hours postdose) | X (24 hours postdose) | |
| Remove vaginal ring/Return test article(s) | | | | | | | X | | |
| Review of daily diary | | | | X | X | X | X | | |
| Discharge from CRU | | | | X (Day 3) | | | | X | |
| Follow-up Phone Call ^g | | | | | | | | | X |
| Adverse events | | | | AEs collected beginning at IVR placement and in on-going manner, as appropriate | | | | | |

CONFIDENTIAL

Table 1.1 Schedule of Assessments and Procedures - IVR Treatment Arm

| Study Procedure | Screening | Pre-Treatment | | 28-Day Treatment Period | | | | | Follow-Up Phone Call |
|------------------------|--|---------------|---------------|--|------------------------|--------|--------|--------|----------------------|
| | Days -28 to -2 | Day -1 | Day 1 Predose | Days 1, 2, and 3 | Days 8, 11, 15, and 22 | Day 28 | Day 29 | Day 30 | |
| Time | | | | 0.5, 1, 2, 4, 8, 12, 24, and 48 hours post insertion | | | | | |
| Serious adverse events | SAEs collected beginning at ICF signing and in on-going manner | | | | | | | | |
| Prior/conmeds | X | X | X | Conmeds collected in on-going manner, as appropriate | | | | | |

Abbreviations: AE = adverse event; BP = blood pressure; conmed = concomitant medication; CRU = clinical research unit; ECG = electrocardiogram; EOS = end of study; FSH = follicle-stimulating hormone; ID = identification; HRT = hormone replacement therapy; IVR = intravaginal ring; PK = pharmacokinetic; PR = pulse rate; RR = respiration rate; SAE = serious adverse event; temp = temperature.

- a. Subjects who elect to undergo washout of prior HRT will be asked to sign the informed consent prior to the start of that washout. Washout periods of 8 weeks will require that Screening not commence until 28 days prior to Day 1.

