diameter placebo IVRs. These rings had the same EVA composition as the DARE-HRT1 IVR but did not include any active hormone components. In addition to evaluating subjects' comprehension of the instructions for use, subjects were also evaluated on their ability to properly insert and remove the rings and were asked to report on the acceptability and tolerability of the IVR. The study demonstrated that the placebo IVRs were safe and well tolerated, in terms of reported adverse events (AEs) and physicians' assessments and evaluation of the vaginal mucosa, vaginal sections, epithelial integrity, epithelial surface thickness, and vaginal color. The most frequently reported AE was vulvovaginal discomfort in 8 of 44 (18.2%) treated subjects. Subjects generally found the instructions provided for the IVR easy to understand, and 32 of 44 (73.7%) subjects were able to successfully insert and remove the IVR. The IVRs were reported to be comfortable by the majority of subjects, with most subjects reporting that the IVR was convenient to use and worked with their lifestyle.

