5.4 Subject Withdrawal

Subjects are free to discontinue the study at any time, for any reason, and without prejudice to further treatment. The investigator may remove a subject if, in the investigator's judgment, continued participation would pose unacceptable risk to the subject or to the integrity of the study data. All procedures for early termination must be completed. Reasons for removal or withdrawal may include:

- Withdrawal of consent
- Administrative decision by the investigator or sponsor
- Ineligibility
- Significant protocol deviation
- Subject noncompliance
- Safety concern by the investigator or sponsor

CONFIDENTIAL

- Lost to follow-up

Subjects who are withdrawn prior to completing all study visits may be replaced.

In the event of a subject's withdrawal, the investigator will promptly notify the sponsor and medical monitor and will make every effort to complete the EOS assessments. All withdrawn subjects with ongoing clinically significant clinical or laboratory findings will be followed until the finding is resolved or medically stable; reasonable attempts will be made to follow-up with subjects.

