6.2 Treatments Administered

Each subject will receive either an IVR or daily oral capsule for 28 days.

The IVR is self-inserted by the subject and is to remain intravaginal for 28 days, with removal of IVR in the CRU on the morning of Day 29. If a subject cannot self-insert the IVR, the site physician will insert the IVR.

Those enrolled in the oral arm (Estrace/Prometrium) will also begin dosing on Day 1, with a last dose on Day 29. Subjects enrolled in the oral arm will be directed to self-administer the medication in the morning with a meal and approximately 240 mL of water, starting on Day 2 through Day 27. Doses will be administered in the CRU each of the mornings of Days 1, 28, and 29 with a moderate-fat breakfast.

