7.5 Safety Assessments

7.5.1 Adverse Events

Subjects will be monitored for AEs from administration of the first dose (insertion of IVR or first oral dose, as applicable) of study drug through the follow-up phone call. Refer to Section 8 for additional details.

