8 ADVERSE EVENTS

An AE is defined as any untoward medical occurrence in a subject administered a pharmaceutical product during the course of a clinical investigation. An AE can therefore be any unfavorable and unintended sign, symptom, or disease temporally associated with the use of a study drug, whether or not thought to be related to the study drug.

Subjects will be monitored throughout the study for AEs, from IVR placement or first oral dose, as applicable, through the follow-up phone call. Adverse events that are identified at the last assessment visit (or the early termination visit) as specified in the protocol must be recorded on the AE eCRF with the status of the AE noted. All events that are ongoing at this time will be recorded as ongoing on the eCRF. All (both serious and nonserious) AEs must be followed until they are resolved or stabilized, or until reasonable attempts to determine resolution of the event are exhausted. The investigator should use his/her discretion in ordering additional tests as necessary to monitor the resolution of such events.

The procedures specified in Section 8.4 are to be followed for reporting SAEs.

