8.2.1 Serious Adverse Events

The investigator is responsible for determining whether an AE meets the definition of an SAE. An SAE is any AE occurring from ICF signing through the follow-up phone call that results in any of the following outcomes:

- Death
- A life-threatening adverse drug experience
- Inpatient hospitalization or prolongation of existing hospitalization
- A persistent or significant disability/incapacity
- A congenital anomaly/birth defect
- An important medical event*

*Important medical events that may not result in death, be life threatening, or require hospitalization may be considered an SAE when, based upon appropriate medical judgment. They may jeopardize the subject and may require medical or surgical intervention to prevent any of the outcomes listed in this definition. Examples of such medical events include allergic bronchospasm requiring intensive treatment in an emergency room or at home, blood dyscrasias or convulsions that do not result in inpatient hospitalization, or the development of drug dependency or drug abuse.

Note: SAEs require immediate reporting to the sponsor and medical monitor. Refer to Section [8.4](#) for details.

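### Non-serious adverse events from ring insertion attempts before placement are not collected, and a randomized woman whose ring is never placed drops out of the safety analysis and may be replaced

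*Combined protocol and SAP*

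**What the plan says.** Safety and tolerability of DARE-HRT1 is a secondary objective (Section 3.2), and AEs are the first secondary endpoint listed (Section 9.4.2).

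- **Population.** Under Section 9.2 a ring subject counts for safety if she is among "all enrolled subjects who received active treatment, i.e., inserted an IVR (and thus who were exposed to one of the IVRs"; an oral subject needs at least one dose.
- **Non-serious AE window.** Table 1.1 has "AEs collected beginning at IVR placement and in on-going manner, as appropriate". Section 8 monitors AEs "from IVR placement or first oral dose, as applicable, through the follow-up phone call". Section 7.5.1 says "Subjects will be monitored for AEs from administration of the first dose (insertion of IVR or first oral dose, as applicable".
- **Serious events.** Section 8.2.1 opens the window earlier: "An SAE is any AE occurring from ICF signing through the follow-up phone call".
- **Fallback.** Section 6.2 says: "If a subject cannot self-insert the IVR, the site physician will insert the IVR".
- **Replacement.** Section 5.4 says: "Subjects who are withdrawn prior to completing all study visits may be replaced". Section 9.1 also lets dropouts be replaced. Neither excludes any reason for leaving.
- **Reporting.** Section 9.6 tabulates treatment-emergent AEs by treatment.

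Randomization precedes treatment (Section 9.3), so a failed insertion is a post-randomization event.

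**The concern.** Whether a ring can be inserted without undue pain is part of its tolerability. If recording starts only when the ring is in place, pain or minor injury on the way there is lost, including in women who end up with a ring after one or more failed attempts. If insertion finally fails, the woman leaves the safety denominator, and the woman who replaces her enters it only if her own insertion succeeds. The ring arms could then look better tolerated than they were. With 10 women per arm, one missing woman visibly changes a percentage.

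The difficulty is foreseeable from the protocol itself. Section 2.1 describes reduced vaginal elasticity and lubrication after menopause, and Section 2.3 names vulvovaginal discomfort as the most frequent AE with the placebo ring (8 of 44).

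**Working it through.** **1. The passages side by side, by situation**

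| Situation | Non-serious AE collected? | In Safety Population? | Replaceable? |
|---|---|---|---|
| Ring placed, later removed for pain | Yes | Yes | Yes |
| Failed attempts, then placed (by the woman or the physician) | From placement only, under Table 1.1 and Section 8. Section 7.5.1 could be read to include the insertion procedure | Yes, provided physician insertion counts; Section 9.2 does not say so explicitly | Not for this reason |
| Self-insertion fails, and physician insertion fails or is declined | No, because there is no placement | No | Yes (Sections 5.4 and 9.1) |

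A serious event is collected in all three rows, because that window opens at consent. The gap is therefore the third row, plus the pre-placement part of the second.

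One further route leads to the third row. Vaginal irritation or tenderness is exclusion criterion 11, Section 5.2 allows discontinuation of a woman who develops an exclusion criterion, and Section 5.4 lists ineligibility as a reason for withdrawal. Irritation caused by an attempt could be recorded under that reason.

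**2. The plan's own figures**

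- Sample size: 3 arms × 10 = 30, of whom 2 × 10 = 20 receive rings. Section 9.1 calls the size empirical and gives no inputs, so there is nothing further to reproduce.
- Section 2.3, discomfort: 8/44 = 18.2%, as printed.
- Section 2.3, insertion and removal: "32 of 44 (73.7%) subjects were able to successfully insert and remove the IVR". In fact 32/44 = 72.7%. This is a separate printing error, and nothing below depends on it.

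**3. Chance that the third row occurs**

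The documents give no rate of never-placed rings after the physician fallback, so the rate *p* is an assumption. Treating women as independent, P(at least one among *n*) = 1 − (1 − *p*)^*n*.

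| Assumed *p* | One arm, *n* = 10 | Both ring arms, *n* = 20 |
|---|---|---|
| 1% | 9.6% | 18.2% |
| 2% | 18.3% | 33.2% |
| 5% | 40.1% | 64.2% |
| 10% | 65.1% | 87.8% |

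For example, 1 − 0.95^20 = 64.2%.

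**4. Effect on the reported figure**

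Suppose *k* women stop at insertion because of pain and are replaced, and nobody else has that outcome. The plan as written reports 0 of 20 overall, or 0 of 10 in an arm. Counting every attempted insertion gives *k*/(20 + *k*) overall, or *k*/(10 + *k*) if all are in one arm. Clopper-Pearson 95% intervals are in brackets.

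- *k* = 1, one arm: 0/10 (0 to 30.8%) becomes 1/11 = 9.1% (0.2 to 41.3%).
- *k* = 1, both arms: 0/20 (0 to 16.8%) becomes 1/21 = 4.8% (0.1 to 23.8%).
- *k* = 2: 2/22 = 9.1% overall, or 2/12 = 16.7% if both are in one arm.

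**The case against.** **Final failure should be uncommon.** Before randomization each woman has a normal pelvic examination with speculum, an endometrial biopsy that yielded tissue and a transvaginal ultrasound. Women with irritation or tenderness are excluded, and ring training is given at screening and on Day 1. Physician insertion then stands behind self-insertion. This stands, and it is why the rates above are kept low and labelled as assumptions.

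**A reader might take the 12 of 44 women without success in the placebo-ring study as the failure rate.** That would give 20 × 12/44 = 5.5 women and 1 − (32/44)^20 = 99.8% for at least one. The documents do not support this use. The figure combines insertion with removal and reflects the women's own attempts. In this trial removal takes place in the CRU, and a physician inserts the ring if the woman cannot.

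**A reader might conclude that such a woman disappears from the safety record.** That is too strong. Serious events run from consent, early terminators have end-of-study procedures (Section 4.1.2), withdrawals are notified to the sponsor and medical monitor (Section 5.4), and the questionnaire goes to all ring subjects (Section 7.5.4). However, the questionnaire is exploratory and scheduled for Day 30, and no section says how data from outside the Safety Population are reported.

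**A reader might see a filter on the ring arms that the oral arm lacks.** Section 9.2 applies the same rule, at least one exposure, to all arms. Only the likelihood of failing at that step may differ.

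**An exposed-subject safety set is conventional, and detail is deferred to a separate statistical analysis plan.** The first part stands: adding women without hormone exposure would dilute drug-related AE rates. The second stands only for reporting. That plan is not among the documents and might cover untreated randomized women, but it cannot recover events that were never collected.

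**Conclusion.** The point holds in limited form. On the wording of Table 1.1 and Section 8, non-serious pain or injury from attempts before placement falls outside the AE window; Section 7.5.1 is open to a wider reading. A randomized woman in whom physician insertion also fails or is declined is outside the Safety Population and may be replaced, and no section requires her to be counted by arm.

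The size depends on an unknown rate that is probably low. Over an assumed 1% to 10%, the chance of at least one such woman among 20 runs from 18% to 88%, and one of them changes an arm's figure from 9.1% to 0. These figures assume independence and full replacement. They do not cover unrecorded pain in women whose ring is eventually placed, for which the documents give no rate.

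The primary pharmacokinetic endpoints are unaffected and no hypothesis is tested. The change is still worth making before the first ring is dispensed, because tolerability is a stated objective and the missing events cannot be reconstructed later.

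**What to change.** 1. In Table 1.1, Section 7.5.1 and Section 8, start ring-arm AE collection at the first insertion attempt, whether by the woman or the physician, and use the same wording in all three places.
2. In Section 9.2, keep the Safety Population as exposed subjects, and state that a ring inserted by the physician counts.
3. In Section 9.6, add a summary by arm, shown next to the tolerability results: randomized women with an attempted insertion, those whose ring was never placed, the reasons and AEs, and any replacements. Women who are replaced stay in this summary.

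The cost is wording in these sections, one extra eCRF field for the attempt and its outcome, and one extra summary. That summary will include women without hormone exposure, so it should be labelled as such and kept separate from AE rates in exposed subjects.

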9.3 Randomization

Upon completion of their screening procedures and confirmation of their eligibility (including an endometrial biopsy, cervical screening test, and transvaginal ultrasound), eligible subjects will be admitted to the CRU on Day -1 and will be randomized. Randomization will occur prior to initiation of treatment. Subjects will be randomized in a 1:1:1 ratio to the treatment groups.

9.4 Endpoints

9.4.1 Primary Endpoints

- C_{ss} and C_{max} for estradiol, estrone, and progesterone for each treatment

9.4.2 Secondary Endpoints

- adverse events
- clinical laboratory findings
- physical examination findings
- vital signs

CONFIDENTIAL

- pelvic examination findings
- vaginal pH and cytology

9.4.3 Exploratory Endpoint

- responses to Usability and Tolerability questionnaire

9.5 Pharmacokinetic Statistical Analysis

The DARE-HRT1 IVR is the test (investigational) product of interest, with two dose combinations of estradiol and progesterone being assessed. Thus, comparisons of the estrogen and progesterone concentrations will be made for each dose combination as DARE-HRT1 IVR versus oral therapy.

The PK analysis will be performed for each IVR dose and assessed versus the oral reference. Graphics will be provided to allow for visual inspection of the mean and individual subject concentration-time profiles.

The PK parameters C_{avg} , C_{ss} , C_{max} , C_{tau} , t_{max} , AUC_{0-24} , AUC_{D1-D30} , and $t_{1/2, eff}$ will be determined from the plasma concentration-time profiles, where possible. Geometric mean values and coefficients of variation (CV%) will be estimated and reported.

If possible, the dose proportionality for the DARE-HRT1 IVR estradiol and progesterone doses will be assessed.

Other details of the PK analysis will be described in a separate Statistical Analysis Plan.

9.6 Safety Analysis

Adverse events, concomitant medications, clinical laboratory findings, physical examinations, pelvic examination with speculum examination and visual vaginal examination findings, endometrial biopsy findings, cervical screening test results, and vital signs for each subject will be tabulated or summarized descriptively, where appropriate.

Vital signs data (observed and change from baseline) will be summarized by time point and treatment using appropriate descriptive statistics. For the safety population, changes from baseline at each post-randomization visit and end of treatment will be compared among treatment arms. Qualitative analysis of laboratory tests in terms of abnormality will be performed. Findings on physical examination will be reported and compared at the screening and end of treatment.

The number and percentage of subjects reporting any treatment-emergent AE will be tabulated by system organ class and preferred term for each treatment (coded using MedDRA). Treatment-emergent AEs will be further classified by severity and relationship to treatment.

CONFIDENTIAL

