2.5 Hypotheses

No formal hypotheses will be tested.

CONFIDENTIAL

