16. Subjects with a history of any severe acute or chronic medical or psychiatric condition or laboratory abnormality that could increase the risk associated with trial participation or study treatment administration or could interfere with the interpretation of trial results and, in the judgment of the investigator, would make the subject inappropriate for entry into the trial. This includes but is not limited to the following:
 - a. Human immunodeficiency virus (HIV) infection (confirmed by medical history/serology testing)
 - b. Active chronic hepatitis B or hepatitis C infection including hepatitis B surface antigen and hepatitis C antigen positive subjects with or without abnormal liver enzymes (confirmed by medical history/serology testing)
 - c. Concurrent neurodegenerative disease
 - d. Cardiovascular: uncontrolled hypertension, unstable angina, myocardial infarction or symptomatic congestive heart failure within the past 6 months, serious uncontrolled cardiac arrhythmia, use of Class 1 antiarrhythmic medications, or history of venous thromboembolism or stroke
 - e. Dementia or significantly altered mental status that would prohibit the understanding or rendering of informed consent and compliance with the requirements of the protocol
 - f. History of gallbladder disease unless gallbladder removed

CONFIDENTIAL

g. Symptomatic bacterial vaginosis

17. Have fasting triglyceride of > 300 mg/dL and/or total cholesterol of > 300 mg/dL
18. AST or ALT > 1.5 times the upper limit of normal
19. Fasting glucose > 125 mg/dL
20. Evidence of current alcohol or drug abuse in the past 60 days including a positive result from the urine drugs of abuse or alcohol screen, or history of drug or alcohol dependence in the last two years, as assessed by principal investigator. Alcohol abuse is defined as greater than 14 standard units/week for females and drug abuse is defined as known psychiatric or substance abuse disorder that would interfere with participation with the requirements of this study, including current use of any illicit drugs.
21. Participation in any other investigational drug or device trial in which administration of an investigational study drug/device occurred within 30 days or placement of a non-drug eluting medical device within 15 days prior to screening.

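### Section 9.6 compares changes from baseline between arms of 10 and names no baseline adjustment, although two vital-sign readings just before dosing are already scheduled in every arm

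*Combined protocol and SAP*

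**What the plan says.** Section 9.1: "A total of 30 healthy, postmenopausal female subjects (n = 10 per arm) are planned for inclusion in this study". The size "is empirically derived, and supported by the PK data obtained from ovariectomized sheep"; no SD, effect size, alpha or power is given. Section 2.5: "No formal hypotheses will be tested".

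Section 9.6 on vital signs: "Vital signs data (observed and change from baseline) will be summarized by time point and treatment using appropriate descriptive statistics". For the safety population it then adds that "changes from baseline at each post-randomization visit and end of treatment will be compared among treatment arms". It does not say how the arms are compared, whether baseline enters as a covariate, or which pre-dose reading is the baseline. Section 7.5.2 defines a baseline (the last value before first dose) for laboratory tests only.

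Section 9.6 on laboratory tests: "Qualitative analysis of laboratory tests in terms of abnormality will be performed". Laboratory findings also stand in the list of data that "will be tabulated or summarized descriptively, where appropriate".

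Tables 1.1 and 1.2 schedule vital signs at screening, Day -1, Day 1 predose, and Days 8, 15, 22 and 30 in all arms. The ring arms have an extra reading on Day 11. Neither table shows vital signs on Day 28 or 29, so the last reading, on Day 30, comes after ring removal or the last oral dose.

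Vital signs and laboratory findings are secondary endpoints (Section 9.4.2). Section 9 leaves the analyses to a separate SAP, and no such text was in the file available for this review.

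**The concern.** Where nothing is tested, the estimated arm difference and its precision are the result. With 10 women per arm, baseline means will differ by chance. A simple change from baseline subtracts the whole of that difference, although only a fraction rho of it is expected to persist to the later visit. The remainder adds noise to the comparison, and the noise in a single baseline reading adds more. Baseline adjustment removes the first part; averaging the two readings taken just before dosing reduces the second.

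At stake is how clearly a shift in, say, blood pressure between the ring and oral arms can be seen. Section 9.6 fixes change from baseline by visit as the quantity to compare, so a SAP that follows it literally would give up precision that costs nothing to keep.

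**Working it through.** The plan states no precision for any safety comparison, so there is no figure to reproduce.

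**Inputs.** 10 per arm (Section 9.1); two readings just before dosing, Day -1 and Day 1 predose (Tables 1.1 and 1.2). Assumed, because the documents give neither: equal correlation rho between all visits, shown at 0.4, 0.6 and 0.8, and a systolic SD of 12 mmHg.

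**Formulas**, per woman in units of SD squared:
- Unadjusted change at one visit from one baseline: 2(1 - rho).
- ANCOVA at one visit on the mean of two pre-dose values: 1 - 2rho²/(1 + rho).
- Ratio of the second to the first: (1 + 2rho)/(2(1 + rho)). It runs from 0.50 at rho = 0 to 0.75 as rho approaches 1.
- SE of a difference between two arms of 10, with V the per-woman variance: SD × √(0.2 × V).
- Cost of estimating the slope: three arms of 10 leave 27 within-arm degrees of freedom, so the variance rises on average by 1/(27 - 2) = 4%, and the SE by about 2%.

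| rho | Change variance | ANCOVA variance | Ratio | Ratio × 1.04 | SE, change (mmHg) | SE, ANCOVA (mmHg) | SE with slope cost (mmHg) |
|---|---|---|---|---|---|---|---|
| 0.4 | 1.200 | 0.771 | 0.643 | 0.669 | 5.9 | 4.7 | 4.8 |
| 0.6 | 0.800 | 0.550 | 0.688 | 0.715 | 4.8 | 4.0 | 4.1 |
| 0.8 | 0.400 | 0.289 | 0.722 | 0.751 | 3.4 | 2.9 | 2.9 |

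After the slope cost, this equals an unadjusted-change analysis with 10/0.669 = 15.0, 10/0.715 = 14.0 or 10/0.751 = 13.3 women per arm.

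**Simulation check.** Three arms of 10 with two pre-dose values gave single-visit variance reductions of 38%, 31%, 26% and 24% at rho 0.3, 0.5, 0.7 and 0.9. The formula with the 4% cost gives 36%, 31%, 27% and 23%.

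**If the two pre-dose readings are closer to each other than to later visits.** They are a day apart, so this is likely. Let their correlation be k and each one's correlation with the later visit be rho. The ANCOVA variance is then 1 - 2rho²/(1 + k). At rho 0.6 the ratio is 0.688 for k = 0.6, (1 - 0.72/1.8)/0.8 = 0.75 for k = 0.8, and 0.80 for k = 1. The limit k = 1 is ANCOVA on a single baseline, with ratio (1 + rho)/2, or 0.70, 0.80 and 0.90 at rho 0.4, 0.6 and 0.8.

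**Laboratory tests.** With only the last pre-dose value as covariate, the single-visit ratio is that same (1 + rho)/2.

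**Averaging Days 8, 15 and 22 (vital signs).** The ANCOVA variance is (1 + 2rho)/3 - 2rho²/(1 + rho), or 0.371, 0.283 and 0.156. The ratio to a single-visit unadjusted change is 0.31, 0.35 and 0.39. Under correlation that decays with time the gain is smaller, and against the Day 8 change alone it can vanish.

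**The case against.** The strongest reply is that Section 9.6 leaves the method open and does not choose a wrong one. It never says that the change is unadjusted, the SAP may specify ANCOVA, and in a Phase 1 PK study with an empirical sample size and no hypotheses, no conclusion hangs on the choice. All of this stands as a limit on importance. It does not remove the point: the protocol names the change at each visit as the quantity compared, leaves the vital-signs baseline undefined, and gives a SAP author no reason to do better.

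A second reply is that an unadjusted change is unbiased under randomisation. That is correct. With SD 12 mmHg, one standard error of the baseline difference is 12 × √0.2 = 5.4 mmHg. At rho 0.6 it carries (1 - 0.6) × 5.4 = 2.1 mmHg into the comparison of changes, but this is already part of the variance of 0.800 above. The argument is about precision, not bias.

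A reader might also count 5 vital signs × 4 visits × 3 arm pairs = 60 comparisons and infer that the plan will produce about three false signals. The documents do not support this: they plan neither intervals nor p-values, and the comparisons share women, visits and arms. The proposed intervals are just as many, so the count argues neither for nor against adjustment.

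**Conclusion.** The point holds as a modest precision gain from data already scheduled. By-visit baseline adjustment leaves about 0.64 to 0.72 of the unadjusted-change variance at rho 0.4 to 0.8 under equal correlation, before the 4% slope cost. The ratio moves towards 0.70 to 0.90 if the two pre-dose readings are nearly interchangeable. The mmHg figures rest on an assumed SD.

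Two stronger readings are not supported. One is that the repeated values would more than halve the variance of every planned comparison. By visit the saving never exceeds half. A larger gain comes from replacing the visits by one average over Days 8 to 22, a different estimand that assumes a roughly constant effect. Day 30 cannot share in it. For laboratory tests with one baseline, even the averaged ratio is (1 + 3rho)/6, which exceeds one half once rho passes 0.67.

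The other is that laboratory data are treated only as normal or abnormal. Section 9.6 also allows them to be summarised descriptively, and its sentence on changes from baseline is not expressly confined to vital signs. Section 5.2 excludes "AST or ALT > 1.5 times the upper limit of normal", so some women may enter above the limit, but they can still normalise and a shift table would show it. What can fairly be said is that no quantitative between-arm laboratory comparison is explicitly specified.

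**What to change.** In Section 9.6, or in the SAP:
- Define the vital-signs baseline for the between-arm comparison as the mean of Day -1 and Day 1 predose.
- Keep the descriptive tables of observed values and changes by visit.
- For each vital sign at Days 8, 15, 22 and 30, compare arms by ANCOVA with arm and that baseline. Report adjusted differences with 95% confidence intervals and no p-values, labelled descriptive and not adjusted for multiplicity. Label Day 30 as after the end of treatment.
- If chemistry and hematology changes are compared between arms, adjust each analyte in the same way for its last pre-dose value. Keep the abnormality analysis.
- Optionally add the average over Days 8, 15 and 22 as a supplementary contrast, stating its constant-effect assumption. It should not replace the by-visit comparisons.

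The cost is a few sentences and a few lines of programming, with no new data or visits.
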